## 1. Summary:

**Background:** Irritable Bowel Syndrome (IBS), a chronic relapsing disorder, is diagnosed by symptom-based criteria in the absence of detectable organic causes. IBS frequently leads to severely impaired health related quality of life. IBS-like symptoms, affecting up to 20% of the population, carry significant costs for sufferers, society and healthcare.

The National Institute for Health and Care Excellence (NICE) directs that a limited number of tests are performed when someone presents with IBS-like symptoms. If these tests are normal, lifestyle modifications or specified medication should be prescribed. However, >50% of patients diagnosed with IBS do not improve with this approach.

This may be because alternative conditions are missed particularly when people have IBS-like symptoms characterised by diarrhoea. Evidence suggests that >75% of these patients have other diagnoses, particularly pancreatic insufficiency, microscopic colitis, small bowel intestinal overgrowth carbohydrate malabsorption or bile acid diarrhoea.

Clinical history taking is inaccurate at identifying the cause for symptoms, whereas targeted investigations diagnose these conditions precisely.

In patients with IBS-like symptoms characterised by diarrhoea, no studies have examined the cost-effectiveness and health benefits of early, more comprehensive investigations.

Data show that nurses using checklists, can assess patients accurately, arrange appropriate investigations and apply treatments effectively achieving improvement in symptoms comparable to gastroenterologists even when patients have complex underlying gastrointestinal disorders.

**Methodology:** This study will assess whether patients with IBS-like symptoms fulfilling Rome IV criteria for diagnosis of mixed constipation/diarrhoea or diarrhoea predominant IBS, presenting to primary care benefit from nurse-delivered care, which includes investigations and management denied by NICE, compared with standard care delivered by a GP following NICE recommendations.

Additionally, an economic analysis will be undertaken examining the costs for patients and healthcare in each arm of the study and a qualitative process evaluation, including semi-structured interviews with the nurses, GPs and a selection of patients, to understand the contextual factors which will facilitate wider application of our approach.

**Research plan:**, After providing informed consent to participate, eligible patients will be stratified by IBS severity and gender, then randomised to care by a GP following NICE guidance or to a research nurse, specially trained to use structured investigations to identify organic pathology and equipped with treatment protocols targeting abnormal investigation results.

Recruitment of 134 patients will give the study 85% power to detect clinically significant improvement in the primary endpoint, IBS severity scoring system (IBSSSS) score at one year allowing for 10% patients loss to follow up and 5% GP deviation from NICE guidance.

## 2. Schedule of events

Procedure	Pre-study assessments	Initial clinic appointment	Initial investigations	Follow up: Initiate treatment or 2nd/3 rd /4th /5 th line investigations (nurses arm only)	Follow up	End of study
Primary Care team referral to the study for IBS-like symptoms	Ö					
Patient contacted, inclusion/ exclusion criteria checked, study explained	Ö					
If interested, information sheet given to patient and contacted 1 week later to confirm on-going interest	Ö					
Consent procedure (including e-consent)	Ö					
Patient symptom self-assessment questionnaire GSRS	Ö			Ö (in nurse led clinic)	Ö (in nurse led clinic)	Ö
Other questionnaires IBS Severity Score (IBS SSS) PHQ-12 SS score SF12 EQ-5D-3L HAD	Ö					Ö
Randomisation	Ö					
Clinical assessment in primary care / or by virtual consultation by Primary care team		Ö		Ö	Ö	
Economic evaluation		Ö	Ö	Ö	Ö	Ö
Qualitative process evaluation					Ö	

## 3. GANNT Chart showing the time lines for the Lincolnshire Poacher Study

Time line				Yea	ar 1			Υ	ear 2			Yea	r 3		
	Before start of	f funding	Start	of fundin	g									End of f	unding
Months of study	-6	-3	0	3	6	9	12	15	18	21	24	27	30	33	36
Pretrial preparation Ethics application R&D Trialling of Patient diary Preparation of checklists/ algorithms Preparation of trial database															
Staff recruitment															
After start of funding Pre-trial staff training Ongoing staff training (monthly with C	1)			-, ,	+ +	+ +	+ + +	+ + +	+ + +	+ + +	+ +	+ + +			
Patient recruitment Patient follow up										_					
Project evaluation process															
Trial management group meetings			1		↓	↓	↓	↓	↓						
Report preparation, writing & result dissemination															
Months of study	-6	-3	0	3	6	9	12	15	18	21	24	27	30	33	36

## 4. Background

This randomised trial aims to assess whether specially trained nurses can improve outcomes for patients presenting for the first time with IBS-like symptoms compared to standard care delivered by a GP. In this study, GPs will follow NICE management guidance for patients with a diagnosis of IBS. The nurses will be trained to follow detailed checklists and a management algorithm which will include additional, mostly non-invasive, well tested investigations which are not included in NICE recommendations but have the ability to identify organic diagnoses which mimic IBS and which would otherwise be missed. The cost of both approaches for patients and healthcare will be measured and trial participants will be followed for one year to assess whether any symptom improvements are maintained.

IBS is defined by symptom-based diagnostic criteria in the absence of detectable organic causes. It is a chronic, often lifelong relapsing disorder in which abdominal pain and /or discomfort is associated with a change in bowel habit or defaecation. The definition of relevant symptoms have been refined over many years at expert consensus meetings. Recently updated criteria termed the "Rome IV" criteria were published in 2016.

Many large studies from primary and secondary care and encompassing different cultures around the world have consistently documented that in the population seeking healthcare, those diagnosed with IBS-like symptoms, a prevalent and expensive condition have a surprisingly poor health related quality of life (HRQoL). Indeed, the HRQoL across most domains is comparable to conditions which carry a high mortality, such as ischaemic heart disease, heart failure and diabetes mellitus.

It is more common in women than men, in lower socio-economic groups and mostly diagnosed in younger patients. Patients with IBS visit the doctor more frequently, use more diagnostic tests, consume more medications, miss more workdays, have lower work productivity, are hospitalised more frequently, and consume more overall direct costs than those without IBS. Resource utilization is highest in patients with severe symptoms and poor HRQoL. Many community-based studies indicate that IBS with diarrhoea predominance or with mixed IBS diarrhoea/constipation are more prevalent than IBS with predominant constipation.

When IBS is associated with intermittent or constant diarrhoea, quality of life is generally lower than when IBS is predominantly associated with constipation. Women with IBS have a lower level of quality of life than men and consistently report higher levels of intestinal and non-intestinal symptoms despite similar levels of IBS severity, abdominal pain, psychological symptoms and illness impact. Distress is highest among younger patients with IBS.

As a result of IBS symptoms, US and UK data suggest that the mean number of days (8.5 - 21.6) lost to work per year[1] is significantly more than for people without IBS and when at work, IBS sufferers have lower productivity. This has economic consequences for both the sufferer and their employer. However, the true costs of this disease for patients and society are poorly characterised.

In the UK, IBS affects up to 20% of the population at any one time although many patients with IBS do not seek medical advice. However, once an individual is diagnosed with IBS, they utilize healthcare services more than people without IBS. It has been estimated that a full time GP sees on average eight patients with IBS a week (one of whom is presenting for the first time)[2] costing the NHS £22 million/year for consultations[3] and more than £70 million

for prescriptions issued afterwards[4]. Whilst the National Institute for Health and Care Excellence (NICE) advises that these patients with typical symptoms of IBS do not require referral to secondary care, nevertheless patients with IBS account for approximately 7.5% of total out-patient attendances in British secondary and tertiary care gastroenterology and colorectal surgical clinics, at a cost of at least £12 million in 2012–2013.[4].

Using the Rome IV criteria as the benchmark for the diagnosis of IBS, in 2017, NICE updated their recommendations that in patients presenting to primary care with typical IBS-like symptoms the following tests should be undertaken to exclude other diagnoses: full blood count, erythrocyte sedimentation rate, C-reactive protein and antibody testing for Coeliac disease.

NICE categorically stated that a number of tests are unnecessary to confirm diagnosis in people who meet the IBS symptom diagnostic criteria including ultrasound, sigmoidoscopy, colonoscopy, barium enema, thyroid function tests and any faecal testing or breath testing.

For patients meeting their criteria for a diagnosis of IBS, NICE acknowledges that while no treatments for diarrhoea predominant IBS are effective in even a majority of patients, some patients respond to a wide variety of treatments: changes in carbohydrate intake, gluten avoidance, wheat free diets, antibiotics, probiotics, antidepressants, opioid receptor agonists/antagonists and some complementary therapies. If these failed to improve symptoms, NICE recommended that consideration should be given to the use of one or more of the following drugs: antispasmodics, laxatives, loperamide, tricyclic or selective seretonin reuptake inhibitor antidepressants [5-12].

However, NICE acknowledge that at least 50% of patients will continue to have unresolved symptoms long term[13, 14] despite following their recommended approach.

The simple conclusion is that patients with IBS-like symptoms are not suffering from a single condition and indeed, the key criticism of the symptom-based approach for the diagnosis of IBS is that symptoms are an unreliable way to distinguish patients with organic treatable pathology from those with true IBS[15].

This is particularly true when patients with IBS-like symptoms have intermittent or persistent diarrhoea. Data from many studies suggest that treatable organic pathologies can be detected in the majority of this patient group[15] if they are investigated more intensively than NICE recommends. The potentially missed diagnoses and the frequency with which they occur in patients meeting the criteria specified by NICE for the diagnosis of IBS are as follows:

1.	Infectious diarrhoea	<1%
2.	Inflammatory bowel disease	<1%
3.	Cancer	<1%
4.	Non-coeliac gluten sensitivity[8]	c5%
5.	Pancreatic insufficiency[5]	7%
6.	Microscopic colitis[6]	10%
7.	Small bowel intestinal overgrowth[7]	40%
8.	Carbohydrate malabsorption[8]	35-64%
9.	Bile acid diarrhoea [9, 10].	25-33%

The best evidence showing that organic diagnoses are frequently missed in this patient group come from patients with a condition called bile acid diarrhoea, which is the cause for

symptoms in 25-33% of patients confidently diagnosed with IBS[9, 10]. Data suggest that almost half of patients diagnosed with bile acid diarrhoea wait for more than 5 years to be diagnosed and many patients report that their symptoms are repeatedly dismissed resulting in a significant adverse effect on their mental health[16]. Failing to diagnose accurately and rapidly carries significant costs. In patients newly diagnosed with bile acid diarrhoea in secondary care, if the correct diagnostic test was requested at the first appointment (one in three patients), the episode of care costs £811.40 whereas if it was booked at a later appointment (two in three patients) the episode of care cost £1,568.31 and of course, delaying correct diagnosis means that patients have to put up with untreated symptoms for much longer[17]. Despite clear evidence that this diagnosis is frequently mistaken for IBS, the scan which accurately diagnoses bile acid diarrhoea remains significantly underused in the UK.

A systematic review investigating the prevalence of small intestinal bacterial overgrowth (SIBO) in patients diagnosed with IBS reported a pooled prevalence of 38% (95%CIs 33-46%). A systematic review of the frequency of pancreatic insufficiency misdiagnosed as IBS suggested a prevalence of 7.1%[5]. Systematic reviews of the efficacy of a low 'Fermentable Oligo-, Di-, Mono-saccharides And Polyols' (FODMAPs) diet or gluten free diets show that the overall quality of the data are very low and although there is benefit in some patients it is difficult as yet to quantify accurately how often carbohydrate malabsorptive syndromes and non-coeliac gluten sensitivity occur[8].

The symptoms produced by the conditions listed above are similar. In a prospective study, albeit in a different patient group, those with new onset gastrointestinal (GI) symptoms after cancer treatment, in whom conditions 5-9 are common, expert clinicians correctly predicted the underlying condition based on GI symptom assessment and history alone in only 24% patients. When more than one diagnosis contributed to symptoms, they never predicted the correct combination of diagnoses[18].

In a recently published randomised controlled trial (RCT) in the Lancet[19] a structured approach to investigating and managing 23 different GI symptoms following a defined checklist of investigations and management algorithms applied systematically was highly effective at improving symptoms. This was in patients with new GI symptoms developing after radiotherapy for pelvic cancer who required on average only 3 appointments and was relatively inexpensive. This was achieved in a condition widely considered to be complex or even untreatable. Furthermore, a trained nurse achieved benefits in most of this patient group, not inferior to those achieved by a consultant gastroenterologist[19].

The ability of nurses to develop skills sufficient to manage patients with specific conditions is unsurprising. Others have shown that 80% cure or improvement is feasible after interventions by specially trained nurses for patients with faecal incontinence. Chronic constipation, straining and evacuation difficulties can also be helped by nurse led treatment, and when patients are not cured, they nevertheless often report they are highly satisfied with their improvement and have greatly improved ability to live with symptoms[20].

In patients with IBS-like symptoms, there have been no prospective studies in primary or secondary care that have examined whether using a comprehensive panel of investigations for likely organic disorders is effective, how much it would cost and whether any health benefits are achieved. Nor has it ever been tested whether nurses following checklists could achieve results equal to or better than those achieved by GPs following NICE guidance.

Although active management of symptoms using algorithms has been tested in two studies in patients with IBS in secondary care, they have been limited in their scope, for example focusing on just one possible diagnostic test - faecal calprotectin[21] - or in second study, investigating a strategy of using endoscopy in addition to the NICE recommended tests. However, the investigations used would not have excluded many of the diagnoses listed above: particularly pancreatic insufficiency, bile acid diarrhoea, small bowel intestinal overgrowth or any carbohydrate malabsorptive syndromes other than lactase deficiency[22].

## 5. Hypothesis

In a common, often debilitating condition which is expensive for patients and healthcare, where no single treatment helps even a majority of patients, there are no reported studies which systematically look to see how many of the patients with IBS-like symptoms which include diarrhoea have one of the many possible organic conditions which produce the same symptoms.

This study will use checklists of investigations and apply treatments systematically, to explore whether patients with IBS-like symptoms characterised by predominant diarrhoea presenting in primary care, benefit from a rigorous management approach using well defined, mostly non-invasive and relatively cheap investigations to make a clear diagnosis of organic conditions which otherwise would be missed if the GP follows NICE recommendations.

The underlying hypothesis is that many patients confidently diagnosed using the ROME IV criteria as having diarrhoea predominant or mixed diarrhoea/constipation IBS in fact have treatable organic diagnoses which are currently missed due to inadequate investigation of GI symptoms.

## 6. Research question, aims and objectives

This study challenges current approaches following NICE recommended treatment options and assesses:

**Research question:** Is nurse-delivered structured care for patients with suspected IBS presenting to primary care clinically effective and cost-effective compared with usual GP care?

**Research aim:** To investigate the effectiveness and cost-effectiveness of nurse-delivered structured care (assessment, investigation using simple test and management of gastrointestinal (GI) symptoms) in patients with suspected IBS in primary care compared with usual GP care.

## **Research objectives**

- a) To investigate the effect of nurse delivered structured care for IBS patients on symptoms and quality of life.
- b) To measure the cost-effectiveness of this approach from a health service perspective.

c) To undertake a process evaluation to explore the feasibility of training nurses to deliver structured care for patients presenting with IBS symptoms, and to understand the fidelity of delivery, contextual factors and barriers and facilitators to wider adoption.

## 7. Study end points

## Primary end point

Improvement in patient symptoms at 1 year measured using the IBSSSS questionnaire

## Secondary end points

- Economic evaluation of the healthcare and patient costs
- Change in quality of life at 1 year
- Time to symptom improvement
- Conditions diagnosed at any time from randomisation to end of 1 year follow up

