## Data of the patient's demographics will be recorded in all patients and include:

- Patient date of birth
- Gender
- Ethnicity
- Occupation
- Alcohol intake as recorded on the summary care record (if available)
- Body Mass Index

- Presence of other comorbidities
- Family history of Coeliac Disease / Inflammatory Bowel Disease (Crohn's /Ulcerative Colitis)/ Bowel cancer and if present which degree relative and at approximately what age was this diagnosed.

In addition, the participants in the trial will be given a questionnaire to complete in which they can enumerate their monthly financial outgoings resulting from their IBS-symptoms and/or consultations/ investigations. Patients will be able to complete these forms on line, over the telephone or on paper each month of the study and the patient will be asked which will be easier for them and if so, how would they like to complete these questionnaires. They will also be asked if they would like to receive a monthly reminder letter/ text/ email/ phone call each month of the study with the next questionnaire. Even if patients have been discharged from clinical follow up, they will be contacted two monthly for 1 year from the date of randomisation to record any health related costs secondary to their IBS symptoms.

The IBSSSS score (mild + moderate v severe) and patient gender (male v female) will be used to stratify the patients via the online randomization system provided by the HHTU.

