## Stratification

## **Analysis**

Means ± SD values or percentiles appropriate to the distribution will be reported for the primary outcome and secondary outcomes by treatment group. A statistical model will be fitted with IBS severity scoring system[23] as the dependent variable. This will be adjusted for baseline assessment of the IBS severity score. A random effects model will be explored. A point estimate, 95% confidence interval and p-value will be reported for the average treatment effect. Residual values will be examined for an approximate normal distribution. If values are highly skewed then a transformation or robust statistical methods will be used instead.

Mixed linear regression models will be used to compare continuous outcomes between treatment groups by adjusting for corresponding metric calculated at baseline and random site effect.

For assessing group difference in demographic covariates, including age, sex and socioeconomic status, linear regression models will be used to compare continuous and ordinal variables, logistic regression will be used to compare categorical variables, and Poisson regression models will be used to compare event rates, while adjusting for a random site effect. For analysis of adverse events, formal statistical comparisons will only be performed when there are enough observed events. If outliers exist, a robust Poisson regression model will be used instead.

Missing data for secondary outcomes will not be imputed. Available case analysis method will be used for secondary analyses.

Two sided p-value will be reported and a 5% significance level will be used to declare statistical significance. For all above mentioned secondary analyses, the false discovery rate will be controlled using the adaptive Benjamini-Hochberg procedure.

A detailed statistical analysis plan will be drafted and approved by the Trial Management Group before data lock.

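### Time to symptom improvement is a secondary endpoint reported by arm, but no symptom score common to both arms is scheduled between baseline and 12 months

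*Protocol*

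**What the plan says.** Section 7 (Secondary end points) lists "Time to symptom improvement" without naming an instrument, a threshold or assessment times. Section 11 (Analysis) states that summaries "will be reported for the primary outcome and secondary outcomes by treatment group", so a comparison between arms is implied.

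The table in section 2 (Schedule of events) fixes what is measured and when:

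- The row "Other questionnaires IBS Severity Score (IBS SSS) PHQ-12 SS score SF12 EQ-5D-3L HAD" is ticked pre-study and at end of study only.
- The GSRS row is ticked pre-study and at end of study, and also in the two follow-up columns, where each tick is qualified "in nurse led clinic".
- The clinical assessment row is ticked at follow-up and names no symptom measure.

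Section 10 describes two contacts during the year that reach both arms. One is a questionnaire in which "they can enumerate their monthly financial outgoings resulting from their IBS-symptoms and/or consultations/ investigations", which patients may "complete these forms on line, over the telephone or on paper each month of the study". The other applies even after clinical discharge: "they will be contacted two monthly for 1 year from the date of randomisation to record any health related costs secondary to their IBS symptoms". Both are described as recording costs. For the GP arm, section 10 arranges a follow-up GP appointment and supplies a summary of NICE management. It specifies no symptom questionnaire.

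**The concern.** A change in symptoms can be dated only when symptoms are assessed. A GP-arm patient who improves in month 2 is first scored at month 12. A nurse-arm patient who improves in month 2 can be scored at the next clinic visit. If those records supply the event times, the arms differ in recorded time because of the measurement schedule and not because of treatment. The direction of that difference is known: it favours the intervention.

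Faster relief is a result that readers would use. Nurses and participants are unblinded (section 9), so nothing else in the design offsets unequal observation. An SAP can define improvement and choose a model, but it cannot create GP-arm scores that were never collected. With one post-baseline score, the GP arm shows whether improvement was present at 12 months, not when it began.

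**Working it through.** **Step 1: which instrument could date improvement?**

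| Instrument | Interim data, nurse arm | Interim data, GP arm | Consequence |
|---|---|---|---|
| IBS-SSS | none scheduled | none scheduled | timing not estimable in either arm |
| GSRS | at nurse-clinic follow-up | none scheduled | nurse-arm dates recorded earlier |
| Clinical assessment or notes | nurse clinic | unstandardised GP notes at most | still unequal |
| Monthly or two-monthly contact | costs | costs | no symptom date |

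No row gives comparable timing in both arms.

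**Step 2: inputs for an illustration of the second case.** The protocol gives no figure for this endpoint.

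- Evaluable patients (section 11, Sample size): 72 severe + 48 mild to moderate = 120, or 60 per arm at 1:1.
- Proportion improving: 50%, the protocol's figure for controls, applied to both arms so that there is no true difference.
- Assumed: exponential improvement times with rate ln(2)/12 per month, so that half improve by month 12; improvement sustained; no measurement error; GP arm scored only at month 12. Nurse visit times are also assumed, because the protocol does not fix them.

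**Step 3: recorded times.** The proportion improved by month t is F(t) = 1 − 2^(−t/12). Each improvement is dated at the next visit.

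- Nurse visits at 3, 6, 9 and 12 months: the proportions first recorded at each visit are 0.159, 0.134, 0.113 and 0.095. The mean recorded time among improvers is (3×0.159 + 6×0.134 + 9×0.113 + 12×0.095)/0.5 ≈ 6.9 months.
- Nurse visits at 6 and 12 months: (6×0.293 + 12×0.207)/0.5 ≈ 8.5 months.
- GP arm: 12 months for every improver.
- True mean among improvers in both arms: about 5.3 months.

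Before month 12, about 40% (three-monthly visits) or 29% (visits at 6 and 12) of the nurse arm is recorded as improved, against 0% of the GP arm.

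**Step 4: false-positive rate.** Simulated log-rank tests, two-sided 5%, no true difference, 5,000 trials per row:

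| Nurse arm scored at | GP arm scored at | Rejections |
|---|---|---|
| 6, 12 | 12 | about 20% |
| 3, 6, 9, 12 | 12 | about 37% |
| monthly | 12 | about 50% |
| 3, 6, 9, 12 | 3, 6, 9, 12 | about 5% |

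In the first three rows almost every rejection favours the nurse arm. With equal schedules the test keeps its nominal level.

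**Step 5: all improvement by month 3.** Suppose exactly 30 of 60 improve in each arm, recorded at month 3 (nurse) and month 12 (GP).

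- Month 3: 30 events, all in the nurse arm, with 60 and 60 at risk. Expected nurse events 30 × 60/120 = 15. Variance 30 × ½ × ½ × 90/119 = 5.67.
- Month 12: 30 events, all in the GP arm, with 30 and 60 at risk. Expected nurse events 30 × 30/90 = 10. Variance 30 × ⅓ × ⅔ × 60/89 = 4.49.
- Observed minus expected: (30 − 15) + (0 − 10) = 5. z = 5/√10.17 = 1.57, p ≈ 0.12.

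When the number improving varies by chance around 50%, the test rejects in about 35% of simulated trials.

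**The case against.** **The instrument is not named.** The only symptom scale tied to an endpoint is the IBS-SSS, which is collected at the same times in both arms. A reader might infer that the comparison is necessarily biased towards the nurse arm. The protocol does not support that. On the IBS-SSS the two arms are treated alike and the endpoint simply cannot be estimated. Bias arises only if GSRS or nurse-clinic assessments supply the dates. This limits the claim of bias, but the endpoint fails either way.

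**GP-arm improvement might be dated from notes.** The clinical assessment row is ticked in the general follow-up column, which is not confined to the nurse arm, so saying that GP-arm improvement can be dated only at month 12 would be too absolute. What the GP arm lacks is a scheduled symptom questionnaire. Dates from notes would be unstandardised. They would change the size of the asymmetry but not remove it.

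**No time-to-event test is specified.** A reader might infer that this endpoint falls within the false-discovery-rate family. Section 11 applies that control to the secondary analyses it has just described, which are linear, logistic and Poisson models. A comparison by arm is implied, but its test and its place in the family are not stated. The log-rank test here is an illustration.

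**A gap of up to nine months in recorded times might suggest near-certain rejection.** It does not. Step 5 gives p ≈ 0.12 at the expected counts and about 35% rejection, because GP-arm events at month 12 partly offset the early nurse-arm excess.

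**It is one of four secondary endpoints.** This stands, and it bears on the severity.

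**Conclusion.** The point holds, and it should be fixed. As scheduled, the endpoint is either not estimable (IBS-SSS) or unequally observed in favour of the nurse arm (GSRS or nurse-clinic assessment), and no later analysis plan can supply the missing GP-arm scores.

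In the second case the error rate rises from a nominal 5% to roughly 20–50%. That range rests on assumed visit times, exponential and sustained improvement in half of each arm, 60 evaluable patients per arm, and a GP arm scored only at month 12. It shows the order of magnitude and is not a forecast. The primary endpoint, measured at baseline and one year in both arms, and the sample size of 134 do not depend on it.

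**What to change.** Collect the same short symptom score at the same fixed times in both arms by adding it to the existing monthly questionnaire or two-monthly contact. One example is the IBS-SSS at months 2, 4, 6, 8 and 10, which fits the two-monthly contact that continues after clinical discharge, with the end-of-study score completing the series. Define improvement on that score, for example a fall of at least 50 points from baseline, which is the protocol's own minimum important difference. Analyse the result as interval-censored or discrete-time data, and do not let extra nurse-clinic scores supply event dates. Update the schedule of events to match.

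If the extra score is not wanted, drop the between-arm comparison and report nurse-arm GSRS over time descriptively.

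The first option costs a small added burden for participants and a minor amendment. The second costs one secondary endpoint. Interim scores not taken at the time cannot be recovered, so the amendment is worth most before follow-up accrues.
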